Figure 1 provides an overview of this 2-arm RCT, involving a behavioral intervention (AWARE) and an AC. A total of 155 YA cancer survivors were enrolled in the study and randomized to AWARE (n=78) vs. AC (n=77). Participants were recruited, screened for eligibility, consented, and asked to complete the baseline survey. Both AWARE and the AC involved an 8-week intervention and control for non-specific intervention components. After the 8-week interventions, participants were immediately asked to complete the end-of-treatment (EOT; 8-week/2-month) follow-up assessment. At 16-weeks post-baseline, participants were asked to complete the final follow-up (FU; 16-week/4-month) assessment.

[figure not shown]

Figure 1. Study Overview

Study Population:

This study focuses on YA cancer survivors, targeting ~150 participants total randomized to AWARE vs. AC (1:1 randomization).

Inclusion Criteria: Inclusion criteria included: 18-39 years old, within 3 years of completing primary treatment or on maintenance chemotherapy, English-speaking, US resident, and smartphone access.

Exclusion Criteria: Exclusion criteria were: cancer recurrence since treatment completion, central nervous system cancer diagnosis (to ensure requisite cognitive functioning), in hospice, and prior diagnoses of alcohol/drug dependency, psychosis, bipolar disorder, or major depressive disorder.

Study Interventions:

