Survey data collection involved ~20-minute web-based assessments (via REDCap) at baseline, end-of-treatment (EOT; 8 weeks post-baseline), and follow-up (FU; 16 weeks post-baseline), with \$50 Amazon e-gift codes for completing each survey (up to \$150 total).

Feasibility and acceptability. Feasibility measures include: 1) accrual (recruitment of n=150); 2) retention at EOT and FU; and 3) program engagement, assessed via electronically captured program data regarding the number of weekly sessions viewed and reflections completed, and coach logs of coaching sessions completed.¹³

Acceptability measures include whether participants would recommend the program to friends who are cancer survivors (yes/no), as well as overall program satisfaction and helpfulness of each component (i.e., weekly educational recordings/transcripts, reflections, coaching, wellness monitoring, resources; 1=not at all to 5=very).¹³ We also asked about program frequency and length (about right, too frequent/long, not enough). We also assessed online program usability (i.e., program was easy to use, various functions were well integrated; 1=strongly disagree to 5=strongly agree; Cronbach's alpha=.90) and quality of coach interactions (i.e., my coach: was helpful, was friendly and warm towards me, showed genuine care about me and my experiences, listened to what I was saying, seemed to understand my thoughts/feelings, made me feel free to express myself, was not critical/judgmental; 1=strongly disagree to 5=strongly agree; Cronbach's alpha=.91). Additionally, we asked participants about alternative coaching channels (e.g., phone, text, email, opt-in for coaching only), barriers to coaching and overall program engagement (providing checklists of potential barriers and open-text fields for each), the program's most relevant or important aspects (open-ended), and potential

changes/additions (open-ended).³³

We pre-defined benchmarks for feasibility and acceptability: ≥75% completion/positive suggested no/minor revisions needed, 50-74% completion/positive required major revisions, and <50% suggested intervention failure.

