Preliminary efficacy outcomes. Hope (primary efficacy outcome) was assessed using the Adult Hope Scale, which includes 4 agency items (e.g., "I energetically pursue my goals") and 4 pathways items (e.g., "I can think of many ways to get out of a jam") with responses (1=definitely false to 8=definitely true) yielding total scores of 8-64 and subscale scores of 4-32 (Cronbach's alpha=.90, .81, and .87).¹⁵

We used 2 measures of QOL (secondary efficacy outcome). To assess cancer-specific QOL, we administered the Functional Assessment of Cancer Therapy – General (FACT-G),³⁴ which includes subscales with 7 items each for physical, functional, and social well-being and 6-items for emotional well-being (Cronbach's alphas=.83, .83, .82, and .75). We also administered the 43-item Patient Reported Outcome Measurement Information System (PROMIS) Global Health Scale V2.0,³⁵ including subscales with 6 items each for physical functioning, fatigue, sleep disturbance, pain interference, ability to participate in social roles/activities, anxiety, and depression (Cronbach's alphas=.90, .94, .91, .96, .95, .93, and .93), and one item for pain intensity.

Covariates. Participants reported sociodemographic characteristics (e.g., age, sex, sexual orientation, ethnicity, race, education level, employment status, relationship status, parental status, health insurance) and cancer diagnosis/treatment factors (e.g., site and stage at diagnosis, treatments, date of diagnosis and treatment completion).

Statistical Analysis Plan:

Sample Size Determination: Assuming 80% power for sample size calculations, we targeted a sample size of n=150 to detect differences across conditions in key measures of feasibility and acceptability. Tests of efficacy in this pilot were secondary;³⁶ nonetheless, this sample size is sufficient to detect medium effects on hope (and secondary outcomes (based on the prior one-arm trial¹³), estimating ≥85% retention.

Data Analysis: Survey data were analyzed descriptively using SPSS V.27 with an alpha of .05. First, descriptive analyses characterized participants, and bivariate analyses (t-tests and ANOVAs for continuous variables, Chi-square tests for categorical) examined sociodemographics, health-related factors, and primary and secondary outcomes in relation to condition to determine any baseline differences.

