Then, bivariate analyses assessed feasibility and acceptability outcomes. Next, responses to open-ended survey questions regarding acceptability were thematically analyzed using inductive analysis. Two coders reviewed responses and determined primary and secondary themes, which were then applied to an initial subset of surveys. The coders compared their codes to identify and resolve any discrepancies and clarify or revise themes and subthemes. After establishing high overall agreement (Kappa's>90%), the 2 coders independently coded the remainder of survey responses. Themes were organized into overarching domains alongside representative quotes.

We then assessed preliminary efficacy. Matched pairs t-tests assessed differences in hope and QOL measures from baseline to EOT and to FU among AWARE and AC participants, respectively. Preliminary bivariate analyses (Pearson correlations for continuous variables, t-tests and ANOVAs for categorical) explored factors associated with our outcome of interest (to identify potentially confounding variables to control for in multivariable analyses). Finally, we conducted multivariable

linear regression using block entry: 1) condition only; 2) condition and key sociodemographics (age, sex, education) and cancer-related factors (i.e., cancer stage, treatments, time since treatment completion); and 3) baseline outcome measures. There were minimal differences across the 3 models with regard to intervention effects; thus, we presented block 2, as baseline randomization yielded no differences by condition in hope or QOL outcomes, and hope and QOL scores over time were highly correlated with their respective baseline scores. We also explored program engagement levels in relation to changes in the primary hope outcome and interactions between baseline hope and condition on hope effects.

Informed Consent Process:

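### No missing-data method is stated, and the named efficacy methods leave out anyone without the follow-up score, which can bias AWARE versus AC at FU if loss relates to earlier hope differently by arm

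*Combined protocol and SAP*

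**What the plan says.** The Data Analysis part of the Statistical Analysis Plan names two methods for hope and quality of life (QOL). Within each arm, "Matched pairs t-tests assessed differences in hope and QOL measures from baseline to EOT and to FU among AWARE and AC participants, respectively". Between arms, it uses multivariable "linear regression using block entry: 1) condition only; 2) condition and key sociodemographics (age, sex, education) and cancer-related factors", and a third block adds the baseline outcome score. Block 2 is the one presented. The reasons given are that the intervention effect changed little from block to block, that the arms did not differ at baseline in hope or QOL, and that later scores were strongly correlated with baseline.

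The plan anticipates loss. Sample Size Determination works by "estimating ≥85% retention", and the feasibility measures include "2) retention at EOT and FU". Under Informed Consent Process, the baseline survey comes before randomisation, so all 155 randomised participants (78 AWARE, 77 AC) should have a baseline score.

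The document gives no analysis set, imputation, repeated-measures model, comparison of lost with retained participants, or missing-data sensitivity analysis. Data completeness appears only as an item of the Data and Safety Monitoring Plan. Observed retention is not reported.

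**The concern.** A matched-pairs t-test needs both scores, and a regression on the FU score needs the FU score. Someone who completes baseline and EOT and then does not return therefore adds nothing to the FU comparison, although two earlier measurements of the same outcome are on file. EOT and FU are then estimated in different subsets of the randomised participants.

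The baseline balance that supports presenting block 2 is not stated for those retained at each visit. The presented model contains neither of the earlier scores that could correct for selective loss.

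Hope is the primary efficacy outcome, and FU is the only assessment after the programme's end-of-treatment survey. At stake is the AWARE versus AC estimate at that visit.

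**Working it through.** **1. The plan's own sample size.** Inputs: "Assuming 80% power for sample size calculations, we targeted a sample size of n=150"; "Survey data were analyzed descriptively using SPSS V.27 with an alpha of .05"; and the statement that "this sample size is sufficient to detect medium effects on hope". The plan gives no number for a medium effect and does not say whether the test is two-sided. I assume 0.5 SD and two-sided.
- Normal formula: n per arm = 2 × (1.960 + 0.842)² / 0.5² = 62.8, so 63, or 126 in total. 126 / 0.85 = 148.2, so 149.
- t-test version: 64 per arm, 128 in total. 128 / 0.85 = 150.6, so 151.

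The target of 150 is reproduced. It is a size for completers: 150 × 0.85 / 2 = 63.75 per arm.

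**2. Expected loss.** 155 × 0.15 = 23.25, so up to about 23 people without an FU score at the planning floor.

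**3. Bias in the FU contrast.** The documents give no SD, correlations or dropout pattern, so these are assumptions. Loss before FU follows logit P(missing) = a + b × z, where z is the standardised earlier hope score and a sets overall loss. Three estimators are compared: completers without the baseline score (as in blocks 1 and 2), completers with it (as in block 3), and a missing-at-random estimate using all visits.
- Set A: 600 trials per scenario, 78 versus 77, SD 10 points, correlations 0.65 to 0.75, about 12 to 16% lost, slope b of size 0.5 or 1. Monte Carlo error is about 0.05 to 0.07 points. Points are divided by 10 to give SD units.
- Set B: 2,000,000 per arm, equal correlations of 0.5 or 0.7, about 85% retained, slope of size 0.7. Paired entries are for correlation 0.5 / 0.7.

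Bias in SD units, true effect 0; in the arm-specific rows the bias favours AWARE:

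| Loss depends on | Set, slope | No baseline | With baseline | All visits |
|---|---|---|---|---|
| EOT hope, AWARE only (low scorers leave) | A, 0.5 | 0.05 | 0.02 | 0.00 |
| same | B, 0.7 | 0.05 / 0.07 | 0.03 / 0.02 | 0.00 |
| same | A, 1 | 0.11 | 0.04 | 0.00 |
| EOT hope, opposite directions by arm | A, 0.5 | 0.10 | 0.04 | 0.00 |
| same | B, 0.7 | 0.10 / 0.14 | 0.05 / 0.04 | 0.00 |
| same | A, 1 | 0.22 | 0.09 | 0.01 |
| Baseline hope, AWARE only | B, 0.7 | 0.05 / 0.07 | 0.00 | 0.00 |
| EOT or baseline hope, same in both arms | B, 0.7 | 0.00 | 0.00 | 0.00 |

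With a true effect of 0.5 SD and the same EOT link in both arms, the estimates are 0.49 / 0.48 without baseline, 0.49 / 0.49 with it, and 0.50 / 0.50 using all visits. In set B the opposite-direction pattern leaves 85% retained in each arm, so equal retention rates would not reveal it.

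**4. Within-arm paired tests.** In set B, loss of low baseline scorers moves the mean change among completers by -0.05 / -0.03 SD. Loss tied to EOT hope moves it by 0.00, given the equal correlations assumed.

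**5. Precision when loss is unrelated to hope (set A).** The SD of the FU estimate is 1.74 points without baseline, 1.34 with it, and 1.31 using all visits. Of the 0.43-point gain, 0.40 comes from using baseline and 0.03 from EOT.

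**The case against.** Several points against this are sound.

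- A reader might infer that the documents say only completers were analysed. They do not. It follows from the methods named together with the silence on missing data. Nor is 23 an observed count; it is the planning floor.
- A reader might infer that any dropout linked to hope biases AWARE versus AC. It does not: a link that is the same in both arms gives no bias under no effect and slight attenuation otherwise. Nothing in the documents shows a link that differs by arm. Comparing retention between arms tests for a difference and does not presume one.
- Disengagement from programme content is a weak explanation for loss between EOT and FU. Both programmes end at 8 weeks, the EOT survey follows at once, and each survey is a separate paid assessment.
- The intervention effect is reported to have changed little across the three blocks. In set A, adding baseline moves the estimate by 2.22 - 0.92 = 1.30 points in the largest scenario and 1.12 - 0.41 = 0.71 in the one-arm scenario at slope 1. The report therefore weighs against the larger figures. The evidence is limited: the size of the change is not given, and under the same assumptions chance alone moves the estimate between models with an SD of about √(1.74² - 1.34²) = 1.11 points. All three blocks also need the FU score and none uses EOT, so their agreement does not test for loss that depends on EOT hope beyond baseline.
- The zero bias of the all-visit model follows from generating loss from observed scores only.
- Efficacy is a secondary objective, and the analysis is already reported in the past tense. A change of model now is post hoc.

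These points limit the size of the concern and how firmly it can be put. They do not supply a missing-data method.

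**Conclusion.** The point holds as a possibility of bias combined with avoidable loss of information. The documents do not demonstrate a bias. The named methods cannot use participants without the score being analysed, no FU model uses the EOT score, and the presented block 2 also omits baseline hope.

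If loss relates to earlier hope differently by arm, the FU contrast can be off by about 0.05 to 0.22 SD without baseline and 0.02 to 0.09 SD with it. The plan's target effect is an assumed 0.5 SD. These ranges rest on assumed slopes of 0.5 to 1 log-odds per SD, correlations of 0.5 to 0.75, no true effect, and loss near 15%. The top of the range needs opposite selection in the two arms and fits poorly with the reported agreement between blocks.

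A reader might go further and conclude that a reported AWARE benefit at FU is spurious. The documents do not support that: they give neither retention nor the characteristics of those lost, so neither the presence nor the direction of bias is known. The change is worth making for a secondary objective; it does not touch the primary feasibility and acceptability aims.

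**What to change.** For hope and each QOL outcome, fit one likelihood-based repeated-measures model to all 155 randomised participants in their assigned arm. Use the baseline, EOT and FU scores, with time, condition-by-time, the sex and age strata and the block 2 covariates. Report the AWARE minus AC contrast with a 95% CI at EOT and at FU. Either hold the baseline mean common to the arms or enter baseline as a covariate, because the precision gain from baseline depends on doing one of these. Multiple imputation using baseline and EOT scores is an acceptable alternative.

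Label the analysis post hoc and show it beside the existing block 2 result. Also report:
- retention by arm at EOT and FU;
- baseline and EOT hope of those retained and those lost at FU, by arm;
- a sensitivity analysis in which missing FU hope scores are imputed and shifted in steps, stating the shift at which the conclusion changes.

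Add a sentence to Data Analysis that states the analysis set and how missing scores were handled in the reported tests.

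The cost is re-analysis of data already held and a wording change, with no new participants or visits; the target of 150 is unaffected. The model brings a missing-at-random assumption, which is why the shift analysis is needed, and the estimate may be less favourable to AWARE.

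### The between-arm efficacy result presented (block 2) omits the baseline score, although the stated high correlation with baseline is a reason to include it; the already fitted block 3 should lead

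*Combined protocol and SAP*

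**What the plan says.** Under Preliminary efficacy outcomes, hope is ranked first among the efficacy measures: "Hope (primary efficacy outcome) was assessed using the Adult Hope Scale", "yielding total scores of 8-64 and subscale scores of 4-32". It is surveyed after baseline at "end-of-treatment (EOT; 8 weeks post-baseline), and follow-up (FU; 16 weeks post-baseline" (Study Schedule and Timeline).

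The Data Analysis section describes linear regression with block entry: condition alone (block 1); then age, sex, education and cancer-related factors (block 2); then the baseline outcome measure (block 3). On which block is reported, it says: "There were minimal differences across the 3 models with regard to intervention effects; thus, we presented block 2". Two further reasons follow. Randomisation left no baseline difference by condition in hope or QOL, and "hope and QOL scores over time were highly correlated with their respective baseline scores". No correlation is given, and the size of the differences between blocks is not stated.

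On the status of these tests, Sample Size Determination says "Tests of efficacy in this pilot were secondary", and Data Analysis says "Survey data were analyzed descriptively using SPSS V.27 with an alpha of .05".

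**The concern.** The reasons given for block 2 do not all point to block 2. Baseline balance means that leaving out the baseline score should cause little bias. A high correlation between baseline and later scores means that leaving it out keeps residual variance that adjustment would remove. Taken together, the two reasons predict similar point estimates in blocks 2 and 3 and a clearly smaller standard error in block 3. Similar effects across blocks therefore do not show that the blocks are equally informative, or that they agree at the .05 level.

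The block was also chosen after the effects in all three had been compared, and the document gives no rule fixed beforehand.

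At stake is how precisely the trial reports the effect of AWARE on the efficacy outcome it ranks first. The Risk/Benefit section says the knowledge gained will be used to design a further hope intervention, and a needlessly wide interval, or an effect reported as not significant, would feed into that design.

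**Working it through.** **Inputs.** From the document: target n = 150, 1:1 allocation, at least 85% retention, alpha .05, 80% power, a medium effect on hope. Assumed, because not stated:
- two-sided testing;
- medium = 0.5 SD;
- hope scored as the scale total;
- baseline correlation r of .6 to .8 for a correlation called high;
- cumulative blocks, so that block 3 keeps the block 2 covariates.

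**1. The plan's own figure.** For 0.5 SD, two-sided .05 and 80% power, the normal approximation gives 63 per arm; 126 / 0.85 = 148.2, so 149. The t-based version gives 64 per arm; 128 / 0.85 = 150.6, so 151. The stated 150 is reproduced. Analysable per arm: 150 × 0.85 / 2 = 63.75, about 64. This calculation takes no credit for baseline adjustment.

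**2. Standard errors.** In SD units and ignoring the covariates, block 2: SE = √(2/64) = 0.177. Block 3: SE = 0.177 × √(1 − r²).

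| r | √(1 − r²) | 95% CI half-width, block 2 | 95% CI half-width, block 3 | Effect detectable at 80% power, block 3 |
|---|---|---|---|---|
| .6 | 0.80 | 0.35 | 0.28 | 0.40 |
| .7 | 0.71 | 0.35 | 0.25 | 0.35 |
| .8 | 0.60 | 0.35 | 0.21 | 0.30 |

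The detectable effect without baseline is 0.50.

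**3. When the blocks disagree with equal estimates.** Then z₃ = z₂ / √(1 − r²), so block 3 is significant once z₂ exceeds 1.96 × √(1 − r²). The block 2 p-value below which block 3 passes .05 is .117 (r = .6), .162 (r = .7) or .240 (r = .8).

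**4. How often they disagree under a true effect.** Simulated regressions at one visit: 64 per arm, 8 covariates explaining 10% of variance, 6,000 draws per setting. Entries are the share of trials in which blocks 2 and 3 fall on opposite sides of .05.

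| True effect | r = .6 | r = .7 | r = .8 |
|---|---|---|---|
| 0.3 SD | .241 | .338 | .437 |
| 0.4 SD | .220 | .293 | .350 |
| 0.5 SD | .137 | .171 | .178 |

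A repeat of the simulation gave 13-45%, the range quoted here. Block 2 alone was significant in .000 to .041 of trials, so the disagreement nearly always has block 3 significant and block 2 not. Power at 0.3 SD was .40-.41 for block 2 and .56-.81 for block 3; at 0.5 SD it was .81-.82 and .95-1.00.

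**5. Does the choice raise the false-positive rate?** Null trials were simulated, keeping only those that match the document's account: no significant baseline difference and block estimates within 0.1 SD of each other (an assumed reading of minimal). The chance that block 2 gives p < .05 at EOT or FU was 0.7-4.9%.

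**The case against.** **Selection and false positives.** A reader might infer that two visits and three blocks, with the block chosen after the results were seen, inflate the false-positive rate or let the investigators pick a favourable result. The documents do not support this. They say that one block was presented, that the blocks differed little and that the arms were balanced at baseline. Under those conditions, block 2 at both visits stays below 5% (step 5). The block shown is also the less powerful one, so the choice does not favour AWARE.

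**Unnamed visit and score.** No lead visit is named, the hope total is only the natural reading, and the number of scores analysed is not given. In a secondary, preliminary analysis this is missing detail, not a separate fault.

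**Meaning of minimal differences.** The phrase may mean that all three blocks led to the same conclusions. If so, the disagreement rates and p-value limits do not apply to this trial. That objection stands. The loss of precision remains.

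**The remedy.** Moving the lead to block 3 after the results are known, when block 3 is more often significant, can look like the practice being criticised. This stands in part. The case for block 3 rests on the correlation with baseline and not on the size of the effect, and showing all blocks lets readers judge.

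**Unseen sources and low stakes.** The cited published trial protocol may name the model, and the outcomes paper, listed as under review, may show more than block 2. Neither is available here. Feasibility and acceptability are the primary objective, so this is a reporting recommendation only.

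**Conclusion.** The point holds as a loss of precision. Block 2 was presented after the three sets of effects were compared, and one of the stated reasons for it favours block 3. With 64 per arm and r of .6 to .8, block 3's standard error is about 0.80 to 0.60 of block 2's. If the minimal differences concern point estimates, the two blocks would disagree at .05 in roughly 13-45% of trials at a true effect of 0.3 to 0.5 SD. If they concern conclusions, the cost is only wider intervals. The likely harm is an imprecise or missed hope effect.

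The size depends on the assumed correlation, since none is reported, and on block 3 retaining the block 2 covariates. No feasibility or acceptability conclusion is affected, and no confirmatory efficacy claim is at issue.

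**What to change.** Report the between-arm difference in the hope total from block 3 as the lead estimate, with 95% CIs at both EOT and FU. Show blocks 1 and 2 beside it, so that readers can check the statement about minimal differences. State the baseline correlations and whether block 3 keeps the block 2 covariates. Mark the choice of block as post hoc unless an earlier dated plan, such as the published trial protocol the document cites, names it.

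The cost is small. All three blocks are described as already fitted. The Informed Consent Process section says the baseline survey was completed before randomisation, so block 3 should lose no one for a missing baseline survey, and it uses one more degree of freedom. The drawback is that the lead changes after the results are known; presenting all three blocks makes this transparent.

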Intervention (AWARE) Condition: AWARE aims to respond to cancer-related goal disruptions,³⁰ which particularly impact YA survivors,²⁻⁴ by enhancing goal-oriented thinking. Specifically, AWARE integrates elements from ACT²¹ and involves: 1) reassessing and reestablishing short- and long-term values-based, meaningful goals; 2) enhancing pathways thinking, including problem-solving skills, recognizing challenges, and reacting with flexibility; and 3) enhancing agency, for example, by promoting coping skills and effectively processing difficult thoughts and emotions in order to maintain motivation and self-efficacy. We hypothesized that AWARE will increase hope (i.e., goal-reorientation, pathways thinking, and agency), which may ultimately promote QOL.³¹ The first 4 AWARE sessions focused mainly on goals: (1) considering the cancer experience and its impact on identity and goals; (2) exploring values, self-identity, and goals; (3) reassessing and reestablishing short- and long-term values-based, meaningful goals across life domains; and (4) applying values and goals in relationships. The subsequent 3 sessions focus on pathways and agency: (5) experiencing and processing uncomfortable thoughts; (6) effectively navigating distressing thoughts and emotions; and (7) the utility of mindfulness and perspective when assessing goals and challenges. The final session (8) provided a program summary, opportunity for reflection, and strategies for ongoing application of program-related skills.

Attention Control (AC) Condition. The AC focused on nutrition and cancer,³² which is well-suited for an AC as it has participant relevance but is unrelated to efficacy outcome (hope). The AC involved an existing 6-session podcast with 3- to 5-minute audio-recordings addressing various nutrition-related topics for cancer survivors from reputable sources (e.g., cancer centers), supplemented with introduction and summary sessions to total 8 sessions.

Study Schedule and Timeline:

Participants were recruited in February–September 2024, with final data collection in February 2025. Participants are involved in an 8-week digital, coach-assisted intervention and asked to complete assessments at baseline and 2- and 4-month follow-up.

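### The efficacy regression is reported without the baseline score although the baseline-adjusted model was fitted; none of the reasons given supports this, and the main cost is precision

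*Combined protocol and SAP*

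**What the plan says.** The Data Analysis part of the Statistical Analysis Plan sets out a linear regression with block entry. Block 1 has condition only. Block 2 adds age, sex, education, cancer stage, treatments and time since treatment completion. Block 3 adds the baseline outcome measure. The text compares all three, so the baseline-adjusted model was fitted.

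Block 2 is the one reported, for three reasons:

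1. "There were minimal differences across the 3 models with regard to intervention effects"
2. "thus, we presented block 2, as baseline randomization yielded no differences by condition in hope or QOL outcomes"
3. "hope and QOL scores over time were highly correlated with their respective baseline scores"

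The section gives no estimates, standard errors, intervals or correlations. It states no rule, set before the results were seen, for choosing among blocks, and it does not name the regression's dependent variable.

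Sample Size Determination puts efficacy in second place: "Tests of efficacy in this pilot were secondary". Hope is nevertheless the named primary efficacy outcome, and improving hope and QOL is the trial's stated secondary objective.

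**The concern.** Each reason fails as a ground for dropping baseline.

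- **Similar effects.** Similar point estimates say nothing about standard errors. At best this is neutral between blocks 2 and 3.
- **No baseline difference.** A non-significant test does not show balance. Even perfect balance would leave the precision gain intact, because that gain comes from explaining outcome variance within each arm.
- **High correlation with baseline.** This is the main reason to adjust. It is not a collinearity problem: the correlation is between a covariate and the outcome, and randomisation makes baseline independent of condition on average.

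In a pilot with a preliminary efficacy aim, the between-arm estimate and its interval are the useful product. The Risk/Benefit section says the knowledge gained will feed the design of a further hope intervention. Reporting the less precise model would make that estimate look more uncertain than the data require. The choice was also made after all three models had been seen, and readers are given nothing with which to check it.

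**Working it through.** **Inputs from the documents.** Target n = 150 and 80% power ("Assuming 80% power for sample size calculations, we targeted a sample size of n=150"); retention of at least 85%; alpha .05; 1:1 allocation, with 78 and 77 randomised.

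**Assumptions, not in the documents.** Two-sided testing; a medium effect means 0.5 SD; baseline-to-outcome correlation r = 0.5, 0.6, 0.7 or 0.8; block 2 covariates explain a share R² = 0.10 of the variance (range 0 to 0.20), equally at baseline and later.

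**Step 1: reproduce the plan's sample size.** For 0.5 SD, the normal approximation gives 63 per arm: 126 / 0.85 = 148.2, rounded up to 149. The t-based calculation gives 64 per arm: 128 / 0.85 = 150.6, rounded up to 151. The stated 150 therefore reproduces without any baseline adjustment.

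**Step 2: precision with no covariates.** Analysed per arm: 150 × 0.85 / 2 = 63.75. The 95% half-width is 1.979 × √(2/63.75) = 0.351 SD. The effect detectable at 80% power is 0.500 SD (t-based).

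**Step 3: dependent variable is the post-baseline score.** Block 2 multiplies the standard error by √(1 − R²) = √0.9 = 0.949:

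- half-width 0.351 × 0.949 = 0.333 SD
- detectable effect 0.500 × 0.949 = 0.474 SD

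Block 3 multiplies further by √(1 − rp²), where rp = (r − R²)/(1 − R²). The small change in degrees of freedom is ignored.

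| r | rp | SE ratio, block 3 / block 2 | SE cut | Half-width (SD) | Detectable effect (SD) | Power for 0.3 SD |
|---|---|---|---|---|---|---|
| Block 2 | – | 1 | – | 0.333 | 0.474 | 43% |
| 0.5 | 0.444 | 0.896 | 10.4% | 0.298 | 0.425 | 51% |
| 0.6 | 0.556 | 0.831 | 16.9% | 0.277 | 0.394 | 57% |
| 0.7 | 0.667 | 0.745 | 25.5% | 0.248 | 0.354 | 66% |
| 0.8 | 0.778 | 0.629 | 37.1% | 0.209 | 0.298 | 80% |

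Sensitivity to R²: with R² = 0 the cuts are 13.4, 20.0, 28.6 and 40.0%; with R² = 0.20 they are 7.3, 13.4, 21.9 and 33.9%.

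**Step 4: dependent variable is the change score (covariates ignored).** A change score already removes part of the baseline variance. Its standard error is proportional to √(2(1 − r)), against √(1 − r²) once baseline is added. The ratio is √((1 + r)/2).

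| r | SE cut | Detectable effect, change alone → with baseline (SD) | Power for 0.3 SD |
|---|---|---|---|
| 0.5 | 13.4% | 0.50 → 0.43 | 39% → 49% |
| 0.6 | 10.6% | 0.45 → 0.40 | 47% → 56% |
| 0.7 | 7.8% | 0.39 → 0.36 | 58% → 65% |
| 0.8 | 5.1% | 0.32 → 0.30 | 76% → 80% |

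**Step 5: does a non-significant baseline test remove the need to adjust?** With 78 and 77, a gap of up to 1.96 × √(1/78 + 1/77) = 0.31 SD is non-significant. A gap of that size would shift an estimate of the post-baseline difference by r × 0.31, about 0.16 SD at r = 0.5 and 0.25 SD at r = 0.8. In 10,000 simulated trials per setting (66 per arm, no other covariates), looking only at those with a non-significant baseline test, power for 0.3 SD was about 40% unadjusted. With baseline adjustment it was 50% (r = 0.5), 66% (r = 0.7) and 81% (r = 0.8). The gain survives apparent balance.

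**Step 6: is there bias or error inflation?** Across all simulated null trials, both the unadjusted and the adjusted analysis had type I error near 5%. Taking whichever of the two was significant raised it to between 7% and 9%. Nothing in the SAP suggests the choice followed significance, so this is a reason to disclose all three models and not a finding against the authors.

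**The case against.** The best defence is that little depends on the choice. The authors report minimal differences in intervention effects, and on a wide reading this could cover intervals and significance as well as estimates. Efficacy is secondary, and the feasibility and acceptability benchmarks do not use this regression. Block 2 is not arbitrary either, since it contains age and sex, the stratification factors. All of this stands, and it limits the consequence: a large shift in the point estimate is unlikely. It does not make the rationale valid. If the correlation really is high and the post-baseline score was modelled, the standard errors should differ visibly.

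Other points stand in part:

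- **The size is unknown.** The cut runs from 5% to 40% depending on r, R² and the dependent variable. At the higher correlations, a change-score model loses only 5% to 8%. The one mention of change near the regression, "We also explored program engagement levels in relation to changes in the primary hope outcome", belongs to a separate exploratory analysis and does not settle the matter.
- **155 were randomised, not 150.** Then 155 × 0.85 / 2 = 65.9 per arm, and the block 2 half-width is 0.327 SD instead of 0.333 SD. The standard error ratios do not change.
- **Unbiasedness has a condition.** It holds for everyone randomised. If dropout depends on baseline score differently by arm, block 2 need not be unbiased among those analysed. That is a further reason to adjust.
- **Switching now is a second choice made with results known.** This is true, and it is why the switch must be labelled and all three models shown.

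**Conclusion.** The concern holds. The SAP fitted the better model and reported a less precise one, for reasons that do not support the choice; one of them argues the opposite. The cost is mainly precision. With the post-baseline score as dependent variable, r from 0.5 to 0.8 and R² = 0.10, the standard error is needlessly large: block 3 would cut it by about 10% to 37%, and the detectable effect would fall from 0.474 SD to between 0.425 and 0.298 SD. With a change score the cut is 13% down to 5%. These sizes rest on assumed correlations and on a dependent variable the SAP does not name; the criticism of the rationale rests on neither. Chance imbalance among those analysed is a lesser issue, probably small given the reported similarity of effects. The point is worth correcting for the hope and QOL results, and leaves the primary objective untouched.

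**What to change.** 1. State the dependent variable of the regression, and report the baseline-to-outcome correlations.
2. Make block 3 (condition, baseline value of the same outcome, and the listed covariates including age and sex) the main between-arm efficacy analysis for hope and each QOL outcome at EOT and FU, with estimates and 95% confidence intervals.
3. Report blocks 1 and 2 the same way as sensitivity analyses, so that readers can check the claim of minimal differences.
4. Replace the arguments from baseline balance and high correlation with a plain statement: block 2 was chosen, and the main model then changed, after all three had been fitted. Label the change post hoc.

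**Cost.** No new data are needed; collection is over ("with final data collection in February 2025"). The SAP speaks of three fitted models but does not list the outcomes and visits covered; any that are missing can be fitted from data in hand. Counting the hope total, four FACT-G subscales and eight PROMIS scores gives 13 outcomes × 2 visits × 3 models = 78 estimates, which is a long table, perhaps a supplement. The outcomes paper is listed as under review, so the change must be carried into that report as well as the SAP.
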